### 5.2.4 Early Withdrawal Assessments

For the analysis, assessments performed at early withdrawal visits will be mapped to the nearest missed visit, using midpoints between visits to window the early withdrawal. If the early withdrawal assessment is mapped to a visit where a scheduled assessment is already present, the scheduled assessment will take precedence, and the early withdrawal assessment will be disregarded (and listed only).

*Table 1: Early withdrawal mapping for scheduled visits of Double-Blind Treatment Phase*

Assessment(s)	Timing of Early Withdrawal Assessment	Mapped Visit
---------------	---------------------------------------	--------------

QMD Ref: Worldwide-TMP-ST-054-1.0_Effective: 12Aug2022	Governing QMD: Worldwide-SOP-ST-026	
Confidentiality Statement		

This document is the property of Worldwide Clinical Trials Inc. and may not be duplicated, copied, altered or removed from company without prior approval from Worldwide Quality Assurance or in compliance with Worldwide Standard Operating Procedures.

Worldwide Clinical Trials Controlled Quality Management Document		
 WORLDWIDE CLINICAL TRIALS	Sponsor:	EIP Pharma, Inc.
	Protocol Number:	EIP21-NFD-504
STATISTICAL ANALYSIS PLAN		

Physical Examination	Day 2 to Day 117	Week 16
	Day 118 to (Last dose+14 days)	Follow-Up
Vital Signs	Day 2 to Day 17	Week 2
	Day 18 to Day 33	Week 4
	Day 34 to Day 61	Week 8
	Day 62 to Day 89	Week 12
	Day 90 to Day 117	Week 16
	Day 118 to (Last dose+14 days)	Follow-Up
Hematology, Chemistry, C-SSRS, NTB, DCFS	Day 2 to Day 33	Week 4
	Day 34 to Day 61	Week 8
	Day 62 to Day 89	Week 12
	Day 90 to Day 117	Week 16
Coagulation, EEG	Day 2 to Day 117	Week 16
CDR-SB, TUG	Day 2 to Day 61	Week 8
	Day 62 to Day 89	Week 12
	Day 90 to Day 117	Week 16
NPI-12	Day 2 to Day 89	Week 12
	Day 90 to Day 117	Week 16
ADCS-CGIC	Day 2 to Day 117	Week 16
MDS-UPDRS	Day 2 to Day 61	Week 12
	Day 62 to Day 117	Week 16

Table 2: Early withdrawal mapping for scheduled visits of Open-Label Extension Phase

Assessment(s)	Timing of Early Withdrawal Assessment	Mapped Visit
Physical Examination	Day 2 to Day 229	Week 32
	Day 230 to (Last dose+14 days)	Follow-Up
Vital Signs	Day 2 to Day 33	Week 4
	Day 34 to Day 61	Week 8
	Day 62 to Day 117	Week 16
	Day 118 to Day 229	Week 32
	Day 230 to (Last dose+14 days)	Follow-Up
Hematology, Chemistry	Day 2 to Day 33	Week 4
	Day 34 to Day 61	Week 8
	Day 62 to Day 117	Week 16
	Day 118 to Day 229	Week 32
Coagulation	Day 2 to Day 229	Week 32

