## 5.2.5 Duration / Study Day / Time

First study day (SD1) is defined as the date of first administration of study drug. Study day will be calculated as the number of days from first administration of study drug.

- date of event – SD1 + 1, for events on or after first administration of study drug
- date of event – SD1, for events before first dose.

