#### **5.10.4.4 Change in MDS-UPDRS3 motor examination (Part III) score**

MDS-UPDRS3 score will be analyzed similar to primary endpoint as described in Section [5.10.2.1](#). Change from baseline will be the dependent variable. The difference in the change from baseline during the double-blind treatment period between the neflamapimod treatment group and placebo with corresponding SE and 2-sided 95% CI will be presented.

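### In SAP Table 1 the MDS-UPDRS early-withdrawal windows and their visit label disagree: either the day limits or the Week 12 label is wrong

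*SAP*

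**What the plan says.** SAP Section 5.2.4 states the general rule: an early-withdrawal assessment is "mapped to the nearest missed visit, using midpoints between visits to window the early withdrawal". If the mapped visit already holds a scheduled assessment, the scheduled one is kept and the withdrawal value is only listed.

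Table 1 turns this into day windows for the double-blind phase. Its MDS-UPDRS row has two windows: Days 2–61 mapped to Week 12, and "Day 62 to Day 117" mapped to Week 16. The other rows that include Week 12 (vital signs; the haematology, chemistry, C-SSRS, NTB and DCFS row; CDR-SB and TUG; NPI-12) all close Week 12 at Day 89 and give "Day 90 to Day 117" to Week 16. In the first three of these the Week 12 window is "Day 62 to Day 89". NPI-12 has the same two mapped visits as MDS-UPDRS and uses Days 2–89 for Week 12.

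Table 2, for the open-label extension, gives MDS-UPDRS Days 2–61 for Week 8 and Days 62–117 for Week 16.

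The mapped value is used as follows: "MDS-UPDRS3 score will be analyzed similar to primary endpoint as described in Section" 5.10.2.1 (Section 5.10.4.4). None of the changes listed in the post-lock addendum touches this row.

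**The concern.** A window should contain the visit it is named after. The one labelled Week 12 for MDS-UPDRS does not. Its upper limit is the Week 8 limit in every Table 1 row that has a Week 8 visit. The row therefore conflicts with the section's own nearest-visit rule and with the rest of its table.

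At stake is which analysis week a withdrawal motor score receives. In the example code of Section 5.10.2.1 time in weeks is not a CLASS variable, so the week enters the model as a number, and a wrong label is a wrong covariate value. By-visit summaries are affected too. A programmer must either follow a row that contradicts the text above it or correct it without a record.

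**Working it through.** **Inputs.** Study day is "date of event – SD1 + 1, for events on or after first administration of study drug" (Section 5.2.5) and a week is 7 days (Section 5.2.6). Windows are those of Tables 1 and 2. Planned size is 160 with 10% dropout (Section 3).

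**Nominal days.** Week w falls on Day 7w + 1:
- Week 8: 7 × 8 + 1 = Day 57
- Week 12: 7 × 12 + 1 = Day 85
- Week 16: 7 × 16 + 1 = Day 113

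**Midpoints (the stated rule).**
- Weeks 8 and 12: (57 + 85)/2 = Day 71
- Weeks 12 and 16: (85 + 113)/2 = Day 99
- Weeks 8 and 16: (57 + 113)/2 = Day 85

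**What the other rows do.** Their upper limits are 61 − 57 = 4, 89 − 85 = 4 and 117 − 113 = 4 days after the nominal visit. The working convention is therefore nominal day + 4, not the midpoint (Day 61 against 71, Day 89 against 99). The other rows also depart from the stated rule, but each of their windows contains its own visit.

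**The MDS-UPDRS row.** The window labelled Week 12 ends at Day 61, which is 85 − 61 = 24 days before Week 12. With visits at Weeks 12 and 16, neither the midpoint rule (cut at Day 99) nor the table's convention (cut at Day 89) gives a cut at Day 61.

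**The two readings.**

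| | Limits wrong | Label wrong |
|---|---|---|
| True visits | Weeks 12 and 16 | Weeks 8 and 16 |
| Supported by | the printed Week 12 label; NPI-12 row | same limits for MDS-UPDRS in Table 2; Day 61 is the Week 8 limit elsewhere |
| Misplaced, table convention | Days 62–89 (28 days) | Days 2–61 (60 days) |
| Analysed at | Week 16 instead of 12 | Week 12 instead of 8 |
| Error in time | 4 weeks late | 4 weeks late |

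If the limits are wrong and the midpoint rule is applied instead, Days 62–99 (38 days) are misplaced.

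**Numbers of subjects.** Dropouts: 10% × 160 = 16. Assume they are spread evenly over Days 2–117 (116 days) and that all have a usable MDS-UPDRS withdrawal assessment.
- Limits wrong, table convention: 28/116 = 24%; 0.24 × 16 ≈ 4 subjects
- Limits wrong, midpoint rule: 38/116 = 33%; 0.33 × 16 ≈ 5 subjects
- Label wrong: 60/116 = 52%; 0.52 × 16 ≈ 8 subjects

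These are upper-end figures, since not every dropout will have the assessment.

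**Does the precedence rule remove the problem?** No. If the limits are wrong, a subject with a scheduled Week 12 value who withdraws on Day 88 has the NPI-12 withdrawal value set aside, while the MDS-UPDRS value from the same visit is kept as Week 16. If the label is wrong, a subject with a scheduled Week 8 value who withdraws on Day 60 has the withdrawal value kept as Week 12, and Week 12 summaries for this scale would consist of withdrawal values only.

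**The case against.** The strongest reply is that this is probably a slip in one label. Table 2 uses exactly these limits for MDS-UPDRS with Weeks 8 and 16. On that reading Days 62–117 to Week 16 follows the table's convention and only the first label needs changing. This stands as a possibility, but it does not make the row right: Days 2–61 would then be analysed at Week 12 instead of Week 8.

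A reader might infer that a withdrawal assessment on Day 85 is wrongly analysed as Week 16. The document supports that only if the Week 12 label is correct. With visits at Weeks 8 and 16, Day 85 is their exact midpoint and Week 16 is what the table's convention gives. A scheduled Week 12 assessment keeps its nominal visit in any case. The 24%, or about 4 subjects, has the same condition.

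A reader might also see harm in values placed up to 113 − 62 = 51 days early, or in motor and NPI-12 scores from one visit landing at different weeks. Neither is distinctive. Table 1 accepts 57 − 2 = 55 days for CDR-SB, 85 − 2 = 83 for NPI-12 and 113 − 2 = 111 for ADCS-CGIC, and it deliberately sends a Day 50 withdrawal to Week 8, 12 or 16 depending on the scale.

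Finally, MDS-UPDRS Part III is exploratory and is not tested for significance (Section 5.10.4). The addendum also removes the treatment-by-time term from the model it borrows. Moving a few values by four weeks should then change the treatment difference little. That is fair, and no effect on a reported estimate has been shown.

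**Conclusion.** The point holds as an internal inconsistency. As printed, the MDS-UPDRS row of Table 1 contradicts the nearest-visit rule and the four other rows with a Week 12 visit, and it is wrong under either reading. Which part is wrong depends on the double-blind MDS-UPDRS schedule, which the SAP does not show.

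The size is small: one exploratory endpoint, a few early withdrawals, and a four-week error in the analysis week. About 4 subjects are affected if the limits are wrong and about 8 if the label is wrong, in both cases assuming 16 evenly spread dropouts with usable withdrawal assessments. The primary and secondary endpoints are not affected. It is worth correcting because the double-blind descriptive and mixed-model tables for this scale are marked as topline output.

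**What to change.** Check the row against the double-blind MDS-UPDRS schedule, then make one of two changes:
- **Visits at Weeks 12 and 16:** use Days 2–89 for Week 12 and Days 90–117 for Week 16, matching NPI-12.
- **Visits at Weeks 8 and 16:** relabel the first window Week 8.

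Either change brings the row onto the table's convention, which itself departs from the stated midpoint rule. Section 5.2.4 should say so, for example by describing the limits as nominal day plus 4 (plus 2 for Week 2).

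The addendum records that the database is locked and the study unblinded, and Section 5 requires later changes to go into a post-lock addendum. The cost is a short addendum entry stating the reason for the choice, plus a rerun of the double-blind MDS-UPDRS Part III outputs (Tables 14.2.3.3.1a and 14.2.3.3.2 and Figures 14.2.3.3.3 to 14.2.3.3.5). The entry should state how many subjects changed analysis visit and give the treatment difference before and after.

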## 5.2.5 Duration / Study Day / Time

First study day (SD1) is defined as the date of first administration of study drug. Study day will be calculated as the number of days from first administration of study drug.

- date of event – SD1 + 1, for events on or after first administration of study drug
- date of event – SD1, for events before first dose.

## 5.2.6 Conversion of Days, Height, and Weight

The following conversion factors will be used to convert days into months or years, or vice versa if needed:

1 week = 7 days,

1 month = 30.4375 days, and

1 year = 365.25 days.

The following conversion factors will be used for height and weight:

1 cm = 0.39370 in, and

1 kg = 2.20462 lb.

## 5.2.7 Conventions for Missing and Partial Dates

It is not expected that there will be any missing dates for events occurring during study conduct. Historical dates such as dates of medical history or prior medications may be missing or partial. Dates (historical or during study conduct) will only be imputed if a full date is needed for a calculation or to support a definition.

All dates presented in the individual subject listings will be as recorded on the Electronic Case Report Form (eCRF).

### 5.2.7.1 Missing / Partial Start / Stop Date of Adverse Events and Concomitant Medications

Missing and partial start and stop date will be imputed for analysis purposes as follows.

#### **Partial or missing stop date will be imputed as follows:**

- If the stop date is completely missing and the event has resolved, or the subject has stopped taking the concomitant medication, the stop date will be imputed as the date of the subject's last clinic visit in the study.
- If only the year is known, the stop date will be imputed as "31-Dec" of that year or as the date of the subject's last clinic visit in the study if in the same year.

QMD Ref: Worldwide-TMP-ST-054-1.0_Effective: 12Aug2022	Governing QMD: Worldwide-SOP-ST-026
Confidentiality Statement	
This document is the property of Worldwide Clinical Trials Inc. and may not be duplicated, copied, altered or removed from company without prior approval from Worldwide Quality Assurance or in compliance with Worldwide Standard Operating Procedures.	

Worldwide Clinical Trials Controlled Quality Management Document		
 WORLDWIDE CLINICAL TRIALS	Sponsor:	EIP Pharma, Inc.
	Protocol Number:	EIP21-NFD-504
STATISTICAL ANALYSIS PLAN		

- If the month and year are known, the stop date will be imputed as the last day of that month unless the stop date corresponds to the same month as the subject's last clinic visit in which case the date of subject's last clinic visit in the study will be used instead.

**Missing start date will be imputed as follows:**

- If the stop date occurs on or after the start of study drug or the event / concomitant medication is ongoing, the start date will be imputed as the date of the first dose of study drug.
- If the stop date occurs before the start of study drug, the start date of the event / concomitant medication will be imputed as the subject's screening date or the stop date of the event / concomitant medication whichever the earlier.

**Partial start date (year present, but month and day missing)**

- If the stop date occurs on or after the start of study drug or the event / concomitant medication is ongoing, and the year is the same as the year of first dosing the start date will be imputed the date of the first dose of study drug. If the year is different from the year of first dosing "01-Jan" will be used.
- If the stop date occurs before the start of study drug, the start date of the event / concomitant medication will be imputed as the "01-Jan" of the same year.

**Partial start date (month and year present, but day missing)**

- If the stop date occurs on or after the start of study drug or the event / concomitant medication is ongoing, the start date will be imputed as the first day of the same month and year unless this partial start date is in same month as the first dose of study drug in which case the date of first dose of study drug will be used.
- If the stop date occurs before the start of study drug, the start date will be imputed as the first day of the month and year of the partial stop date.

If the start time is missing it will be imputed only in the case where the start date of the concomitant medication / event corresponds to the date of the first dose of study drug. The time will be imputed as the same time as the first dose of study drug. In all other cases the time will not be imputed.

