### 5.2.11 Adverse Events

A treatment-emergent Adverse Event (TEAE) is defined as one that started, or worsened in severity or seriousness, following the first dose of study drug. An AE with onset prior to the start of administration of the first dose of study drug, or when the stop date is before the start of the administration of the first dose of study drug, or when the study drug was not started, will be considered as pre study. In case the onset date is on the same day as the first dose of study drug

QMD Ref: Worldwide-TMP-ST-054-1.0_Effective: 12Aug2022	Governing QMD: Worldwide-SOP-ST-026
Confidentiality Statement	
This document is the property of Worldwide Clinical Trials Inc. and may not be duplicated, copied, altered or removed from company without prior approval from Worldwide Quality Assurance or in compliance with Worldwide Standard Operating Procedures.	

Worldwide Clinical Trials Controlled Quality Management Document		
 WORLDWIDE CLINICAL TRIALS	Sponsor:	EIP Pharma, Inc.
	Protocol Number:	EIP21-NFD-504
STATISTICAL ANALYSIS PLAN		

and either the time of first dose or time of AE onset is missing, then AE is considered treatment-emergent.

TEAEs starting after first dose of study drug in the double-blind treatment phase and before the first dose of study drug in the open-label extension phase will be summarized under the Double-Blind summary. TEAEs starting after first dose of study drug in open-label extension phase will be summarized under the open-label extension phase.

Maximum severity (Severe) will be assumed for an AE with missing severity.

A treatment-related AE is defined as an AE as being possibly related or related to the study drug. If an AE has missing relationship it is assumed to be related to the study drug for analysis purposes.

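### Missing and partial AE start dates are imputed from the double-blind first dose only, so some open-label events are counted in the double-blind safety tables

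*SAP*

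**What the plan says.** Section 5.2.5 gives each subject one anchor date: "First study day (SD1) is defined as the date of first administration of study drug".

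Section 5.2.7.1 imputes start dates from it when the event stopped on or after the start of study drug or is ongoing:

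- Start date fully missing: "the start date will be imputed as the date of the first dose of study drug".
- Year only, same year as first dosing: "the start date will be imputed the date of the first dose of study drug". Where the year differs, 1 January of that year is used.
- Month and year: "the start date will be imputed as the first day of the same month and year unless" the month is that of the first dose of study drug, in which case that dose date is used.

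Section 5.2.11 then divides the phases at a different date, which it names separately. TEAEs that start after the double-blind first dose and "before the first dose of study drug in the open-label extension phase will be summarized under the Double-Blind summary"; those starting after the first OLE dose go to the OLE summary.

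Section 5.2.7 expects no missing dates for on-study events but provides the rules in case there are some. The post-lock addendum adds one date rule, for a missing date of last dose, and leaves the start-date rules alone.

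**The concern.** Phase depends on the start date, yet no start-date rule uses the date that separates the phases. Placing an uncertain onset at first dose is cautious in a single-phase trial, because it makes the event treatment-emergent. In a trial with a placebo-controlled phase followed by an open-label phase, it can carry the event into the wrong phase.

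The OLE approach document confirms that subjects who had placebo in the main study took active capsules in the OLE. If such a subject's OLE event is back-dated, the double-blind tables show an event on open-label neflamapimod as one under blinded placebo. If a former-neflamapimod subject's OLE event is back-dated, it enters the active double-blind column. In both cases the OLE tables lose an event. What is at stake is the integrity of the randomised AE comparison and of the OLE counts; paired double-blind and OLE tables are planned for each AE summary in section 10.

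**Working it through.** The plan states no figure on this point, so there is none to reproduce. The check applies the rules of 5.2.7.1 and then the phase rule of 5.2.11 to events whose true onset is in the OLE.

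**Inputs from the SAP:** double-blind phase 16 weeks, 16 × 7 = 112 days (section 6); OLE 32 weeks, 32 × 7 = 224 days (last visit in 5.2.4 Table 2 and 5.2.10); planned arm size 80 (section 3).

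**Assumptions, not from the SAP:** first dose on each day of one calendar year; first OLE dose 112 days later (113 and 126 also tried); true onset uniform over the OLE; a 112-day OLE as an alternative; stop date after first dose, or event ongoing.

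**When an event moves.** It moves if the imputed date is before the first OLE dose.

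- Blank start date: the imputed date is the double-blind first dose, which always precedes the first OLE dose. It always moves.
- Year only: it moves if the year is that of first dosing, or if 1 January of the recorded year precedes the first OLE dose.
- Month and year: it moves only if the recorded month is that of the first OLE dose and that dose was not on the 1st. In a month of L days with a uniform start day, the average number of affected OLE days is (L − 1)/2. For L = 30 that is 14.5 days, and 14.5/224 = 6.5%.

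**Full enumeration, 112-day gap, share of OLE-onset events moved:**

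| Date recorded | 224-day OLE | 112-day OLE |
|---|---|---|
| Blank | 100% | 100% |
| Year only | 69% (39% same-year rule + 30% 1 January rule) | 85% (54% + 30%, before rounding) |
| Month and year | 6.6% | 13% |

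Gaps of 113 and 126 days leave the totals for the 224-day OLE unchanged at this rounding.

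**Worked cases.**

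- First dose 11-Mar-2024, first OLE dose 01-Jul-2024, true onset 20-Sep-2024. Blank gives 11-Mar-2024: double-blind, more than six months early. Year 2024 gives 11-Mar-2024: double-blind. September 2024 gives 01-Sep-2024: stays in the OLE.
- First dose 06-Nov-2023, first OLE dose 26-Feb-2024, true onset 10-May-2024. Year 2024 gives 01-Jan-2024, before the OLE: double-blind. May 2024 gives 01-May-2024: stays in the OLE. An onset later in February 2024 with the day missing would become 01-Feb-2024: double-blind.

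**Size per event.** 1/80 = 1.25 percentage points on one arm's rate for a term. This is a maximum: 5.12.1 counts a subject once per term, so a subject who already had that term in the double-blind phase adds nothing. For k moved events in different subjects, same term and same arm, the maximum is k × 1.25 points. The SAP gives no value for k.

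**The case against.** Four points on the other side deserve weight.

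1. **Few dates will be incomplete.** Section 5.2.7 expects none for on-study events, and recorded dates stay visible in the listings. This stands, and it keeps the point minor. But 5.2.7.1 exists for the exceptions, and for those it gives a wrong phase.
2. **Scope.** A reader might infer that any OLE event with an incomplete date is moved back. The rules do not say that. A date with month and year stays in the OLE in every month except that of the first OLE dose, and a year-only date moves often but not always. Within the OLE start month nearly all such events move (29 of 30 start days fall after the 1st), but that month is a small part of the OLE.
3. **Direction.** A reader might infer that the rule flatters neflamapimod by loading the placebo column. The same rule moves former-neflamapimod subjects' OLE events into the active column, and it takes no account of arm. Net bias would need a difference between arms in incompletely dated OLE events, and the SAP gives no such figure.
4. **Column.** Section 5.3 keeps subjects under the same treatment group in both phases, so a former-placebo subject may be labelled placebo in the OLE tables as well. The error is therefore in the phase, not in the label alone.

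One could also argue that the first-dose anchor is meant to restart in the OLE, since Table 2 in 5.2.4 appears to count days from OLE start. The SAP nowhere says so, and 5.2.11 uses a separate, qualified term for the first OLE dose. At best, two programmers could place the same event in different phases.

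**Conclusion.** The defect holds, in limited form. Following 5.2.7.1 and 5.2.11 as written places an OLE-onset AE in the double-blind summary in three situations:

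- always, if the start date is blank;
- with year only, if that is the year of first dosing or its 1 January precedes the first OLE dose;
- with month and year, only if the month is that of the first OLE dose and that dose was not on the 1st.

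The randomised safety comparison is contaminated and OLE counts are reduced. The documents do not support a claim of net bias in favour of the drug; the direction is unknown. The effect is at most about 1.25 percentage points per moved event on the planned arm size, and the number of such events is unknown and probably small. The percentages for year-only and month-year dates depend on the uniform-timing assumption; the list of situations does not. This is a minor point, worth correcting because the correction is cheap.

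**What to change.** Add to 5.2.7.1, for AEs in subjects who entered the OLE: if the AE was first reported at a visit after the OLE-start visit, and the known date parts do not exclude onset on or after the first OLE dose, impute the start as the later of the first OLE dose date and the first day of the known month or year. In all other cases, including AEs already reported at or before the OLE-start visit and AEs with a stop date before the first OLE dose, the existing rules apply.

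Add to 5.2.11 that an AE whose start is imputed to the first OLE dose date counts as an OLE TEAE. Without this, such an event has no phase, because the present wording covers only starts before or after that dose.

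With both changes, the share of OLE-onset AEs first reported after the OLE-start visit that moves back is 0% for all three kinds of incomplete date. Leave the concomitant medication phase rules in 5.8 unchanged: a medicine started in or before the double-blind phase and ongoing in the OLE is already counted in both.

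**Cost:** two sentences and a few lines of derivation code, entered through the addendum route that section 5 sets for changes after database lock. The rule needs the visit at which each AE was first reported; the SAP does not describe that field, so its availability is an assumption. **Downside:** a double-blind event reported late with an incomplete date could be placed in the OLE. To make this visible, list all AEs with imputed start dates near the phase boundary.
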